#### **Statistical Methods:**

Efficacy: All efficacy analyses will be performed on the full analysis set. All analyses will be conducted separately by treatment arm. Patients will be analyzed descriptively and stratified by locally advanced or metastatic cSCC. The 2 treatment arms will be compared descriptively.

For investigator assessed- ORR (primary efficacy variable), number and percentage of responders will be displayed per treatment arm along with its 95% confidence interval according to Clopper-Pearson.

Statistical inference will be based on the thresholds defined by the Simon's 2-stage design. At the final analysis, the null hypothesis of an ORR of  $\leq$ 5% will be rejected if >3 patients out of a total of 29 patients respond (CR/iCR/PR/iPR). In the case of dropouts, appropriate statistical methods will be applied to correct for the deviation from the planned sample size.

Number and percentage of patients per RECIST tumor response category will be displayed for each scheduled tumor assessment time point.

Safety: All safety analyses will be performed on the safety analysis set.

Number of TEAEs, SAEs, and adverse events of special interest (AESIs) with a MedDRA System Organ Class and Preferred Term will be assessed. Number and percentage of patients with a TEAE, SAE, or AESI for IFX-1 (Arm A) and for IFX-1 and pembrolizumab (Arm B) will be assessed.

Where adverse events (AEs) are grouped by NCI CTCAE grade or relationship, the maximum grade/relationship per patient and class of AE will be considered. Analyses will be performed for the treatment period and the follow-up period separately.

Safety laboratory, vital signs, and 12-lead electrocardiogram parameters will be analyzed by summary statistics for absolute values and changes from baseline by visit. Shift tables comparing baseline and the worst post-baseline assessment will be prepared if applicable.

Categorical safety parameters will be summarized by absolute and relative frequencies by time point.

InflaRx IFX-1

Pharmacokinetics and pharmacodynamics: Actual PK sampling times will be determined, and IFX-1 plasma concentration assessed by time point. Summary statistics will be provided for the PK concentrations of IFX-1 at all measured time points including the geometric mean and its coefficient of variation. PK and pharmacodynamics parameters will be analyzed descriptively.

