## 10. STATISTICAL CONSIDERATIONS

# **10.1.** Sample Size Determination

This study plans to enroll a total of up to approximately 70 patients, including up to 29 patients in Arm A to receive IFX-1 monotherapy and up to 41 patients in Arm B (safety run-in: 9 to 18 patients; Phase II portion: 23 patients) to receive combination therapy with IFX-1 and pembrolizumab.

The 2 treatment arms are evaluated separately. No adjustment for multiplicity will be performed for the application of Simon's 2-stage design in each arm. The sample size of 29 for analyses of the Phase II portion in each treatment arm is based on an optimal Simon's 2-stage design, with 10 patients planned for the first stage and 19 patients planned for the second stage. This sample size is based on a proportion of responders for a drug which is not worth to pursue further of  $p_0=5\%$ . The proportion of responders of a good drug was set to  $p_1=20\%$  for this sample size. The null hypothesis that the best ORR  $p\le0.05$  will be tested versus the alternative hypothesis that p>0.05. This design leads to an expected sample size of about 18 patients per arm and a probability of early termination of 59.9%. If the drug is actually not effective, there is a 4.7% probability of concluding that it is effective (Type I error). If the drug is actually effective, there is a 19.9% probability of concluding that it is not effective (Type II error). After testing the drug on 10 patients in the first stages of both arms, the study will be terminated if no patient responds. If a treatment arm proceeds to the second stage, a total of 29 patients (10 in Stage 1 plus 19 in Stage 2) will be studied for this dose in this treatment arm. If the total number responding is  $\le 3$ , the hypothesis of a potentially effective drug is rejected.

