## 10.3.1. Efficacy Analyses

All efficacy analyses will be performed on the FAS. All analyses will be conducted separately by treatment arm. The 2 treatment arms will be compared descriptively. Patients will be analyzed descriptively and stratified by locally advanced or metastatic cSCC.

The primary efficacy variable is the best ORR (investigator assessed) based on modified RECIST v1.1 criteria (Eisenhauer et al., 2009) and iRECIST criteria (Seymore et al., 2017). The number and percentage of responders will be displayed per treatment arm along with its 95% confidence interval according to Clopper-Pearson.

Patients who discontinue the study after assignment to treatment due to 1 of the following reasons will be counted as non-responder if they have not shown response before discontinuation:

- Lack of efficacy
- AE at least possibly related to study treatment
- PD/iCPD
- Clinical deterioration

Statistical inference will be based on the thresholds defined by the Simon's 2-stage design. For decision criteria at the interim analysis, please refer to Section 10.3.4. At the final analysis, the null hypothesis of an ORR of  $\leq$ 5% will be rejected if >3 patients out of a total of 29 patients respond (CR/iCR/PR/iPR). Due to dropouts, the number of patients evaluable for the primary endpoint might not be exactly 29. In this case, appropriate statistical methods will be applied to correct for the deviation from the planned sample size of 29 evaluable patients (Koyama and Chen, 2008). In this case, appropriate statistical methods will be applied to correct for the deviation from the planned sample size of 29 evaluable patients (Koyama and Chen, 2008). Further details will be specified in the SAP.

Additionally, the number and percentage of patients per RECIST tumor response category will be displayed for each scheduled tumor assessment time point.

Secondary Endpoint	Statistical Analysis Methods

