## 10.3.4. Interim Analyses

#### 10.3.4.1. Formal Interim Analysis Based on Simon's 2-Stage Design

An interim analysis based on Simon's 2-stage design (Simon, 1989) of treatment response will be performed after Stage 1 in both treatment arms (monotherapy Arm A and combination therapy Arm B) before enrollment into Stage 2.

The interim analysis will be performed on the first 10 patients evaluable for the Phase II portion per arm when these 10 patients have performed their third post-baseline tumor assessment OR discontinued treatment. At the time of the interim analysis, a treatment arm will be discontinued if 0 responders are observed in the respective treatment arm. A responder is defined as in Section 10.3.1. Each treatment arm will be evaluated separately such that it may occur that enrollment into both arms is stopped, enrollment into 1 arm is stopped and the other is continued to the second stage, or enrollment into both arms is continued. If both arms are discontinued after Stage 1, the final analysis will be performed after all patients enrolled in Stage 1 will have completed or discontinued the study and described in a clinical study report. If enrollment is stopped, patients will still receive treatment until disease progression (EOT), or are discontinued due to other reasons, and will then be followed up for 12 months.

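### The only interval named for the primary response rate ignores the Stage 1 stop, so with exactly 29 evaluable patients no reported result agrees with the test at 4/29, and upper limits at 1 to 3 of 29 are low

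*Combined protocol and SAP*

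**What the plan says.** The synopsis (Statistical Methods) and Section 10.3.1 name the same interval for the primary endpoint; in the words of Section 10.3.1: "The number and percentage of responders will be displayed per treatment arm along with its 95% confidence interval according to Clopper-Pearson". Neither says two-sided; I read 95% as 2.5% in each tail.

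The data come from a two-stage design. Section 10.3.4.1 provides that "a treatment arm will be discontinued if 0 responders are observed in the respective treatment arm" at the interim analysis of the first 10 patients. In Section 10.3.1 the null hypothesis of a rate of 5% or less "will be rejected if >3 patients out of a total of 29 patients respond (CR/iCR/PR/iPR"). Section 10.1 makes the test one-sided (the null "will be tested versus the alternative hypothesis that p>0.05") and states its level: for an ineffective drug "there is a 4.7% probability of concluding that it is effective (Type I error").

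Section 10.3.1 makes the thresholds govern: "Statistical inference will be based on the thresholds defined by the Simon's 2-stage design". It cites a published method for inference from Simon two-stage designs, but ties it to one situation: "Due to dropouts, the number of patients evaluable for the primary endpoint might not be exactly 29". Further detail is left to the SAP. The supplied text contains no separate SAP.

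**The concern.** Clopper-Pearson limits are exact for a fixed number of patients. Here the final number is 10 or 29, depending on the Stage 1 count. Read literally, an arm with 28 evaluable patients gets a two-stage correction and an arm with exactly 29 does not, although the same stopping rule applied to both.

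At stake is how the primary result reads. A reader who sees a rejected null beside limits that include 5% needs to know which result matches the test. A reader of a weak arm, with 1 to 3 responders, may take the upper limit as firmer evidence against activity than the design gives.

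**Working it through.** **Inputs.** Sections 10.1, 10.3.1 and 10.3.4.1: n1 = 10, stop at 0, N = 29, reject at 4 or more, p0 = 5%, p1 = 20%.

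**Formula.** For a total of t ≥ 1, the probability of continuing and reaching at least t is

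S(p, t) = P(Bin(29, p) ≥ t) − (1 − p)^10 × P(Bin(19, p) ≥ t).

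**1. The plan's own figures.**
- Type I error: S(0.05, 4) = 0.05475 − 0.5987 × 0.01324 = 0.05475 − 0.00792 = 0.0468 (stated 4.7%).
- Power: S(0.20, 4) = 0.8596 − 0.1074 × 0.5449 = 0.8011, so type II error 19.9% (as stated).
- Early stop under p0: 0.95^10 = 59.9%. Expected size: 10 + 0.4013 × 19 = 17.6 (stated about 18).

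The design reproduces. The first term alone, 0.0548, is the single-stage p-value at 4/29; the subtracted 0.0079 is the effect of the Stage 1 stop.

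**2. Limits.** Clopper-Pearson 95%: beta quantiles, lower Beta(0.025; t, 30 − t), upper Beta(0.975; t + 1, 29 − t). Two-stage 95%: lower limit L solves S(L, t) = 0.025, upper limit U solves 1 − S(U, t + 1) = 0.025; for 90%, use 0.05. This ordering ranks every continuing arm above one stopped at 0/10, then ranks by total. The ordering is my choice; the documents state none.

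| Responders | Clopper-Pearson 95% | Two-stage 95% |
|---|---|---|
| 1/29 | 0.1% to 17.8% | 0.3% to 30.9% |
| 2/29 | 0.8% to 22.8% | 1.1% to 31.2% |
| 3/29 | 2.2% to 27.4% | 2.4% to 32.2% |
| 4/29 | 3.9% to 31.7% | 4.1% to 34.3% |
| 5/29 | 5.8% to 35.8% | 6.0% to 37.1% |
| 8/29 | 12.7% to 47.2% | 12.8% to 47.4% |
| 0/10 | 0 to 30.8% | 0 to 30.8% |

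From 8/29 on, the two differ by less than 0.2 points.

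**3. The boundary, 4/29.** Lower limits, with method and level varied separately:

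| | 95% | 90% |
|---|---|---|
| Clopper-Pearson | 3.9% | 4.85% |
| Two-stage | 4.1% | 5.1% |

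Only the two-stage limit at 90% (5% per tail) lies above 5% and agrees with the rejection. Changing the level alone or the method alone is not enough. At 5/29 the 95% Clopper-Pearson lower limit is already 5.8%, and the disagreement is gone.

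**4. How often.** Exactly 4/29 occurs in 3.4%, 14.3%, 17.3% and 12.0% of arms at true rates of 5%, 10%, 15% and 20%. A continuing arm ends with 1 to 3 responders in 36.2% of cases at a true rate of 10% and in 9.2% at 20%.

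**5. Coverage of Clopper-Pearson under the design**, summed over the stop at 0/10 and totals 1 to 29: 98.8% at 5%, 97.9% at 10%, 97.8% at 15%, 97.6% at 20%, 98.0% at 30%. On a 0.01-point grid the minimum up to 30% is 96.4%. Coverage is below 95% only from 31.67% to 32.53%. At 31.67% the misses are 0.0222 (stop at 0/10, upper limit 30.8%), 0.0198 (totals 1 to 4) and 0.0195 (high totals), which leaves 0.9385 (0.93848 before rounding, hence 93.8%). At 32% the same interval covers 95.6% for a fixed sample of 29 but 93.9% under the design, so the stopping rule causes the dip. The two-stage 95% interval stays at or above 95.1% throughout.

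**The case against.** The strongest reply is that nothing depends on this interval. The thresholds govern, so Clopper-Pearson is descriptive. At rates of 5%, 10% and 15% both methods have the same coverage, and both over-cover at 20%. The two-stage interval is wider at low counts and makes weak arms look less negative. A 95% interval beside a one-sided test at about 5% is a common convention, and nothing obliges a displayed interval to invert the test. Section 10.3 calls itself a summary, and the SAP may already add what is missing.

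Most of this stands. It limits the weight of the point and reduces coverage to a minor argument. Two parts do not stand in full. The convention explains only part of the disagreement at 4/29, because a 90% Clopper-Pearson interval also includes 5%. And the deferral to the SAP follows the correction for numbers other than 29, whereas Clopper-Pearson is already fixed in two places.

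A reader might infer that the type I error is inflated or that an arm could be wrongly declared active. The documents do not support that: the stated 4.7% and 19.9% reproduce exactly. A reader might also infer that the interval is generally too narrow. It is conservative over the range for which the trial was designed.

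**Conclusion.** The point holds as a low-cost improvement to reporting. The plan's only stated interval for its primary endpoint is not the one that corresponds to its design or its test. The effect is visible at 4/29, where no single-stage result agrees with the rejection, and at 1 to 3 of 29, where the upper limits lie 13.1, 8.4 and 4.8 points below the two-stage ones. No go/no-go decision changes.

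It would be tempting to conclude that a two-stage 95% interval by itself restores agreement at 4/29. It does not: its lower limit is 4.1%.

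The figures assume exactly 10 and 29 evaluable patients, the ordering given above, and a responder status that is the same at the interim and final analyses. The last is an idealisation. Sections 5.2.1 and 5.2.2.2 base continuation on the third tumor assessment without confirmation, while Section 8.2.2 counts best response up to end of treatment or progression, and patients in a stopped arm may stay on treatment. A late responder would turn 0/10 into 1/10, and the identity of the two intervals at 0/10 would no longer apply.

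**What to change.** In the SAP, for each arm that completes Stage 2, including when the evaluable number is exactly 29:

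- Report the two-stage p-value and the two-stage 95% interval (4.1% to 34.3% at 4/29), and state the ordering of outcomes used.
- Add the two-stage 90% interval (5.1% to 30.8% at 4/29) or the one-sided 95% lower limit (5.1%), labelled as the one that corresponds to the one-sided test.
- Keep Clopper-Pearson as a labelled descriptive interval.
- For an arm stopped at 0/10, keep 0 to 30.8%, and say what is reported if a response appears after the interim.

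The cost is SAP wording and a few lines of code, in line with the kind of method the protocol already cites. Sample size and thresholds stay as they are. The price is more than one interval to explain, and higher upper limits at 1 to 3 of 29.

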# **5.4.3.** End of Study Definition

The EOS for the individual patient is defined as the date of the last contact of the 12 months follow-up period, date of death, date of consent withdrawal from study participation (see Section 5.4.4), or the date of last contact when patients are lost to follow-up (see Section 5.4.5).

The entire study will end when all patients have discontinued IFX-1 and IFX-1 + pembrolizumab treatment, AND all patients ended the study as described above.

The sponsor may prematurely terminate the study at any time earlier than planned for the following reasons:

- Unacceptable toxicity
- Administrative reasons

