# 5.4.5. Lost to Follow-Up

A patient will be considered lost to follow-up if he or she repeatedly fails to return for scheduled visits and the study site is unable to make contact as described below.

The following actions must be taken if a patient fails to return to the study site for a required study visit:

- The site must attempt to contact the patient and reschedule the missed visit as soon as possible and counsel the patient on the importance of maintaining the assigned visit schedule and ascertain whether or not the patient wishes to and/or should continue in the study.
- Before a patient is deemed lost to follow-up, the investigator or designee must make every effort to regain contact with the patient (where possible, 3 telephone calls and, if necessary, a certified letter to the patient's last known mailing address or local equivalent methods). These contact attempts should be documented in the patient's medical record.
- Should the patient continue to be unreachable, he/she will be considered to have withdrawn from the study with a primary reason of lost to follow-up.

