# 8.2.2. Evaluation of Overall Response

The best overall response is the best response recorded from the start of the study treatment until EOT or documentation of disease progression according to RECIST v1.1/iRECIST (PD/iCPD). The patient's best overall response assignment will depend on the findings of both target and non-target disease, appearance and size of new lesions, and clinical stability (see Appendix 4). For patients discontinuing treatment for other reasons than PD/iCPD, the tumor assessments will continue during the follow-up period (also see the SoA, Table 1).

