# 10.2. Analysis Sets

For purposes of analysis, the following analysis sets are defined:

Analysis Set	Description
Enrolled Set	All patients who sign the informed consent form
Safety Analysis Set (SAS)	All patients assigned to study treatment and who received
	≥1 dose of study treatment (IFX-1 for monotherapy arm,
	IFX-1 or pembrolizumab for combination arm)
Full Analysis Set (FAS)	All patients assigned to study treatment
Per Protocol Set (PPS)	All patients who received ≥1 dose of study treatment and
	who have ≥1 post-baseline tumor assessment

Protocol violations will be reviewed in the data review meeting. The decisions will be documented in the meeting minutes and finalized before database lock.

In general, safety analyses will be based on the SAS. The primary efficacy analyses will follow an intention-to-treat concept and will be performed on the FAS.

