# **10.3.** Statistical Analyses

The statistical analysis plan (SAP) will be developed and finalized before the first patient is enrolled. The SAP will include the exact definition of endpoints and variables to be analyzed, extensive details on the statistical analysis methods to be used together with the structure of tables and figures to be included as end-of-text tables and figures as well as appended listings for the clinical study report. It will also describe procedures for accounting for missing, unused, and spurious data. This section is a summary of the planned statistical analyses of the primary and secondary endpoints.

Individual data will be listed. Data will be summarized using suitable descriptive statistics; depending on the structure of the data, summary statistics (e.g., number of observations, mean, standard deviation, minimum, median, maximum, lower quartile, upper quartile) or frequency tables may be used.

All data will be displayed by treatment arm if not specified otherwise.

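### The primary ORR is placed on an all-assigned, intention-to-treat FAS, yet Section 10.3.1 lets dropouts change the number analysed and gives no counting rule for non-responders who leave for unlisted reasons

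*Combined protocol and SAP*

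**What the plan says.** Section 10.2 defines the FAS as all patients assigned to study treatment, with no evaluability condition, and states: "The primary efficacy analyses will follow an intention-to-treat concept and will be performed on the FAS". Section 10.3.1 and the synopsis repeat that all efficacy analyses use the FAS.

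Section 10.3.1 then adds two things:

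- Patients who leave the study "due to 1 of the following reasons will be counted as non-responder if they have not shown response before discontinuation". The four reasons are lack of efficacy, an adverse event at least possibly related to treatment, PD/iCPD and clinical deterioration.
- "Due to dropouts, the number of patients evaluable for the primary endpoint might not be exactly 29". In that case a published correction for two-stage designs is to be applied, with details left to the SAP.

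The synopsis has a parallel sentence, "In the case of dropouts, appropriate statistical methods will be applied to correct for the deviation from the planned sample size", but names no method and has no non-responder rule.

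Other exits are foreseen elsewhere. Section 5.4.3 ends an individual's participation at, among others, "date of death, date of consent withdrawal from study participation (see Section 5.4.4), or the date of last contact when patients are lost" to follow-up. Section 5.4.5 says of an unreachable patient that "he/she will be considered to have withdrawn from the study with a primary reason of lost to follow-up". None of these is on the list in 10.3.1 as such.

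The word evaluable is defined neither in 10.3.1 nor in 10.3.4.1, where the interim analysis uses the first 10 evaluable patients per arm.

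**The concern.** An all-assigned denominator is fixed once patients are assigned. A sentence that lets dropouts change the number evaluable for the primary endpoint therefore contradicts the stated analysis set. The four-reason list adds to the doubt. If every FAS patient without a response were a non-responder, neither the list nor the dropout correction would be needed. Together they suggest, without saying so, that a non-responder leaving for another reason is not evaluable.

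Under that reading the removal is one-sided. A response seen before exit still counts, so only patients without a response can drop out of the denominator. In an open-label, investigator-assessed, single-arm comparison with a fixed 5%, the error always favours the drug. For exits due to an adverse event, the investigator's relatedness call would decide whether the patient is in the denominator at all.

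**Working it through.** **Inputs.** From Section 10.1: p0 = 5%, p1 = 20%, 10 patients in stage 1 and 19 in stage 2, stop if no response in stage 1, stated type I error 4.7% and type II error 19.9%. From Section 10.3.1: reject if more than 3 of 29 respond, with Clopper-Pearson 95% limits. The number of patients removed is an assumption, because the documents give no dropout rate.

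**1. The plan's own figures.** With X1 ~ Bin(10, p) and X2 ~ Bin(19, p):

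- Early termination at 5%: 0.95^10 = 0.599. Expected size: 10 + 19 × (1 − 0.599) = 17.6.
- Type I error = Σ P(X1 = x) × P(X2 ≥ 4 − x) for x = 1, 2, 3, plus P(X1 ≥ 4). At 5%: 0.3151 × 0.0665 + 0.0746 × 0.2453 + 0.0105 × 0.6226 + 0.0010 = 0.0468.
- The same sum at 20% gives power 0.8011, so the type II error is 0.199.

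All stated figures are reproduced. The design arithmetic is not in question.

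**2. Who could be affected.** Section 8.2.2 says "The best overall response is the best response recorded from the start of the study treatment until EOT or documentation of disease progression". A patient with SD or PD already recorded therefore has a best overall response and is plainly a non-responder. Under Section 5.4.1, stopping treatment is not leaving the study, and patients who stop without progression continue tumour assessments. The gap is chiefly a study exit, for an unlisted reason, before any post-baseline assessment.

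**3. Effect on the estimate.** For x responders of n, the lower limit is the 2.5% point of Beta(x, n − x + 1) and the upper limit the 97.5% point of Beta(x + 1, n − x). With x = 4, the smallest number that rejects:

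| Removed (assumed) | n | ORR | 95% CI |
|---|---|---|---|
| 0 | 29 | 13.8% | 3.9 to 31.7% |
| 1 | 28 | 14.3% | 4.0 to 32.7% |
| 2 | 27 | 14.8% | 4.2 to 33.7% |
| 3 | 26 | 15.4% | 4.4 to 34.9% |
| 5 | 24 | 16.7% | 4.7 to 37.4% |

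**4. Effect on the decision.** The question is whether 3 responders could suffice with fewer evaluable patients, keeping 10 in stage 1.

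- Unconditional two-stage size of a cut-off of 3: 0.135 at n = 29, 0.098 at 24, 0.062 at 19 and 0.055 at 18. It falls below 0.05 only at 17 (0.048).
- Conditional check, comparing the stage 2 tail at the attained size with the planned conditional error (an assumed form of the cited correction, whose source is not available here). With 1 response in stage 1 and 2 in stage 2, the planned conditional error is 0.0665. The attained tail is 0.0712 at n = 19 (no rejection) and 0.0572 at n = 18 (rejection). With 2 + 1 or 3 + 0 responses there is no rejection at 18 or 19.

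The cut-off of 4 therefore holds for 19 to 29 evaluable patients by both calculations. At 18 the answer depends on the method.

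**The case against.** The strongest reply is that Section 10.3 calls itself a summary and defers to the SAP, of which it says: "It will also describe procedures for accounting for missing, unused, and spurious data". No separate SAP text is in the document reviewed. The four reasons are not stated to be exhaustive, so the SAP could make non-response the default. It is also fair that evaluable appears only in the paragraph on the Simon inference, so the ORR and its interval may be meant to stay on the full FAS. This stands in part: the protocol does not say that unlisted exits leave the ORR denominator. But a SAP default would leave the dropout sentence in conflict with the FAS in both 10.3.1 and the synopsis. If only the test used the smaller number, the estimate and the test would have different denominators.

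A second reply is that the interim is partly covered. Section 10.3.4.1 is triggered by the third assessment or by treatment discontinuation, so early leavers need not have a scan. That is right, and only a short clarification is needed there.

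A reader might infer more than the documents support:

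- *That the type I error is inflated.* Replacing unlisted non-responders until 29 are evaluable would raise it to 5.4%, 6.3%, 7.4% or 8.7% at assumed loss rates of 5, 10, 15 or 20%. The documents do not provide for replacement.
- *That the trial's conclusion could flip.* The cut-off is stable over 19 to 29. With 4 responders the lower confidence limit passes 5% at 22 evaluable patients, but 10.3.1 bases inference on the Simon threshold, not on that limit.
- *That a smaller p-value would be reported.* For 4 responders the unconditional two-stage tail is 0.043 at 28 and 0.035 at 26, against 0.047 at 29. The protocol does not say that this calculation would be used.

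**Conclusion.** The concern holds as an internal conflict in the definition of the primary analysis: an intention-to-treat FAS on one side, a dropout-dependent evaluable number and an incomplete non-responder rule on the other. If unlisted exits were treated as non-evaluable, the bias could run only upward. Its likely size is small: about 0.5 percentage points for one removal and 1.0 for two (13.8% to 14.3% or 14.8%), with 4 responders among 29. The go/no-go rule does not move for 19 to 29 evaluable patients. These sizes rest on assumed numbers of removals and on 10 patients in stage 1. It should be fixed because the denominator of the primary endpoint ought to be settled before data are seen, in a trial where the investigator both assesses response and judges relatedness.

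**What to change.** In Section 10.3.1:

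- Replace the four-reason list with one rule: every FAS patient without a documented CR/iCR/PR/iPR is a non-responder, whatever the reason for leaving.
- Use that one denominator for the ORR, its Clopper-Pearson interval and the Simon rule.
- Delete the sentence that lets dropouts change the evaluable number, and align the synopsis.
- Keep the cited two-stage correction only for actual over- or under-enrolment.

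In Section 10.3.4.1, state that no patient is excluded from the first 10 for lacking a tumour assessment. An evaluable-only ORR on the Per Protocol Set can be added as an optional sensitivity analysis.

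With 29 assigned, the stated 4.7% and 19.9% then hold without a dropout correction, provided that the 5% and 20% are read as rates of documented response among all assigned patients. The cost is a few sentences, with no change to sample size or conduct. The downside is that the reported ORR may be slightly lower than an evaluable-only figure.
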